## 10.3.3 Secondary Outcomes

The trial will have an 80% probability of observing at least one instance of any class of adverse event expected to occur in at least 1.2% of individuals receiving inosine. The trial will have 80% power to detect increased risk of any class of adverse event among subjects receiving inosine if the true risk is two-fold higher and the expected proportion among placebo subjects is at least 14% or if the true risk if four-fold higher and the expected proportion among placebo subjects is at least 3.4%. The trial has 80% probability of declaring serum urate elevation tolerable if the true proportion tolerant under the definition given in Sec. 10.2.2.2 at 12 weeks and 24 months is at least 62%.

The estimated SE for symptomatic effects on UPDRS I-III total scores during wash-in between the moderate elevation and placebo arms in the SURE-PD trial was 0.53 units / month. With n=25 subjects per treatment group in SURE-PD, the expected SE for estimating symptomatic effects in this trial will be roughly sqrt (25/135) \* 0.53 = 0.23 units / month. With that SE, the trial would have 80% power to detect symptomatic effects on the order of a difference in slopes during wash-in or wash-out of 0.65 units/month.

The Kaplan-Meier product-limit estimate from the SURE-PD trial of the proportion of placebo subjects requiring dopaminergic therapy by 24 months was 62%. Assuming constant hazard at the same rate among placebo subjects in this trial during period 1 (0 to 24 months) and 8% loss to follow-up prior to determining need for dopaminergic therapy, the trial will have 80% power to detect a hazard ratio of 0.62. Extrapolating to 27 months, we expect a total of 67% of placebo arm subjects to have disability warranting dopaminergic therapy at the end of period 2 (24 to 27 months). The study would have 80% power to detect a difference in the proportion of subjects with disability warranting dopaminergic therapy if 50% or fewer of active arm subjects have progressed by the end of the trial.

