3.2 Efficacy Outcomes

Additional efficacy outcomes will include time to disability warranting dopaminergic therapy, the prescribed levodopa equivalent dosage (LEDD), motor function as measured by MDS-UPDRS part III, ambulation subset, and patient-reported sections (IB and II), striatal DAT binding by DaTscanTM, cognition as measured by MoCA, mood as measured by Neuro-QOL Depression, quality of life as measured by PDQ-39, and functional disability as measured by modified Schwab and England. Measures of parkinsonian symptoms assessed by the MDS-UPDRS will be analyzed in two ways: (a) excluding assessments completed after initiation of dopaminergic medication, and (b) adjusting for time-dependent LEDD.

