3.6 Two-period Evaluations

Analysis of the persistence of benefit after the 3-month wash-out of period 2 among subjects randomized to active treatment during period 1 permits an evaluation of disease-modifying effect of serum urate elevation. Not all measures are amenable to two-period evaluation because of the censoring effect of initiation of dopaminergic therapy. In particular, with only one-third of subjects expected to have not initiated dopaminergic therapy at the end of period 1, few data on uncensored MDS-UPDRS trajectories during wash-out will be available and subjects contributing those data are a non-random subset of slow progressors. For LEDD-adjusted analysis of MDS-UPDRS and other measures that are equally evaluable at the end of both periods, a three-part test of significantly slower worsening during period 1, non-inferior rates of worsening during period 2, and a significant net benefit at the end of period 2 would provide evidence of disease modification if all three evaluations were favorable.

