3.8 Sample Size

urate. Early, largely untreated PD subjects with a serum urate of <5.9 mg/dL at baseline from DATATOP (n=155; double-placebo only), PRECEPT (n=446) and SURE-PD (n=25; placebo only) were followed for up to two years. The overall UPDRS rate was obtained by weighting each estimate by the inverse of its standard error.

Power for the primary outcome of rate of change in MDS-UPDRS I-III total score is based on a random slopes model with shared baseline. The model will include fixed effects of time, treatment x time, sex, sex x time, an indicator of baseline MAO-B inhibitor use, and baseline MAO-B inhibitor use x time and random site- and subject-specific intercepts and slopes, each with unstructured covariance. MDS-UPDRS assessments completed after a subject has initiated dopaminergic therapy will be censored.

Based on applying the same primary analysis model to data from SURE-PD, the following variance components were estimated for UPDRS I-III total scores: site-level variance (intercept = 9.75, slope = 0.0123 / month, covariance = -0.346), subject-level variance (intercept = 77.4, slope = 0.230 / month, covariance =2.87), and residual variance = 13.9. We assume that 70% of subjects will initiate dopaminergic therapy based on experience in SURE-PD plus up to 8% additional lost to follow-up prior to initiating dopaminergic therapy. With the planned schedule for MDS-UPDRS assessments (screening, baseline, 3 weeks, 6 weeks, 12 weeks, and then

quarterly through 24 months), the variance and censoring estimates above imply an effective standard deviation for UPDRS I-III total score slopes of 0.587 units / month or 0.758 units / month on the scale of MDS-UPDRS I-III total scores.¹²

Given a standard deviation of 0.76 units / month, a final two-sided test at alpha = 0.046 allowing conservatively for two interim analyses at alpha = 0.001 each, the study would have 80% power with n = 270 subjects randomized 1:1 to placebo or urate elevation if the true effect of treatment were to reduce the rate of increase in MDS-UPDRS I-III total score by 6.3 points over 2 years.

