3.9 Power for Secondary Outcomes

The trial will have an 80% probability of observing at least one instance of any class of adverse event expected to occur in at least 1.2% of individuals receiving inosine. The trial will have 80% power to detect increased risk of any class of adverse event among subjects receiving inosine if the true risk is two-fold higher and the expected proportion among placebo subjects is at least 14% or if the true risk if four-fold higher and the expected proportion among placebo subjects is at least 3.4%. The trial has 80% probability of declaring serum urate elevation tolerable if the true proportion tolerant under the definition given in Sec. 3.4 at 12 weeks, 12 months, and 24 months is at least 62%.

The estimated SE for symptomatic effects on UPDRS I-III total scores during wash-in between the moderate elevation and placebo arms in the SURE-PD trial was 0.53 units / month. With n = 25 subjects per treatment group in SURE-PD, the expected SE for estimating symptomatic effects in this trial will be roughly sqrt (25/135) * 0.53 = 0.23 units / month. With that SE, the trial would have 80% power to detect symptomatic effects on the order of a difference in slopes during wash-in or wash-out of 0.65 units/month.

The Kaplan-Meier product-limit estimate from the SURE-PD trial of the proportion of placebo subjects requiring dopaminergic therapy by 24 months was 62%. Assuming constant hazard at the same rate among placebo subjects in this trial during period 1 (0 to 24 months) and 8% loss to follow-up prior to determining need for dopaminergic therapy, the trial will have 80% power to detect a hazard ratio of 0.62. Extrapolating to 27 months, we expect a total of 67% of placebo arm subjects to have disability warranting dopaminergic therapy at the end of period 2 (24 to 27 months). The study would have 80% power to detect a difference in the proportion of subjects with disability warranting dopaminergic therapy if 50% or fewer of active arm subjects have progressed by the end of the trial.

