6.6.8 Symptomatic Effects

The presence of symptomatic effects will be tested using a change-point model constructed as a partial linear spline over time with knots at 12 weeks and 24 months. Both fixed and subject-specific random terms for intercept, slope from baseline to 12 weeks, slope from 12 weeks to 24 months, and slope from 24 to 27 months (or from V10-equivalent visit on study drug to SV) will be included. Unstructured covariance will be assumed among the random effects (10 terms). The AT sample will be analyzed. Significantly smaller slopes during wash-out among subjects treated with inosine using one-sided testing at alpha = 0.025 will be interpreted as symptomatic effects. If symptomatic effects are not found on that basis, the absence of symptomatic effects will be judged based on a non-inferiority test using a non-inferiority bound of 6.3 / 3 = 2.1 points/month in the direction of a symptomatic effect and using one-sided testing at alpha = 0.05.

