6.8.7 Blindedness

Descriptive stats will be summarized for responses on the early and late administrations of the Blindedness Questionnaire and the change between them. The following predictors of treatment assignment belief reported on the Blindedness Questionnaire will be tested by logistic regression. For belief of inosine assignment (stratified by correct and incorrect):

- age at baseline (categorized as <65 years vs. ≥ 65 years)
- sex
- treatment assignment
- MDS-UPDRS I-III censored change at wash-in (per 6.6.8) for response at the 6-week (V02) administration
- MDS-UPDRS I-III censored change to \sim 24-mo/V10 for response at the \sim 24-mo/V10 administration
- history of preceding nephro-lithiasis TEAE
- history of preceding gout, gout-like or other arthritic TEAE
- average preceding daily number study drug capsules
- expectation of inosine: "A lot better" vs "Somewhat better" vs "No change" or worse (Q2 on PD-Expectancy questionnaire),
- expectation of inosine-placebo difference: >/=2 vs <2 units more favorable for inosine (Q2 - Q1 on PD-Expectancy questionnaire)
- preference for inosine: "strong" vs other (Q3 on PD-Expectancy questionnaire).

7. References

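### The stated 80% power for a 0.65 units/month symptomatic effect holds for wash-in but not for a wash-out analysis that excludes scores after dopaminergic therapy

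*SAP*

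**What the plan says.** SAP 3.9 takes the phase 2 standard error for the symptomatic effect during wash-in (0.53 UPDRS units/month with 25 per group) and multiplies it by sqrt(25/135) to obtain 0.23. It then claims 80% power for "symptomatic effects on the order of a difference in slopes during wash-in or wash-out of 0.65 units/month". Protocol 10.3.3 makes the same claim for a "difference in slopes during wash-in or wash-out of 0.65 units/month".

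Other sections describe who will still be untreated at wash-out:

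- SAP 3.6 plans "with only one-third of subjects expected to have not initiated dopaminergic therapy at the end of period 1" and warns that uncensored MDS-UPDRS data during wash-out will be scarce and will come from slow progressors.
- SAP 3.8 assumes that "70% of subjects will initiate dopaminergic therapy based on experience in SURE-PD plus up to 8% additional lost to follow-up" before starting therapy.
- SAP 3.9 itself says "we expect a total of 67% of placebo arm subjects to have disability warranting dopaminergic therapy at the end of period 2".

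SAP 3.2 plans two analyses of MDS-UPDRS symptom measures: "a) excluding assessments completed after initiation of dopaminergic medication, and (b) adjusting for time-dependent LEDD". SAP 6.6.8 tests symptomatic effects in the as-treated sample with a change-point model, at one-sided alpha 0.025. If no effect is found, it tests for absence against a bound of 2.1 points/month at one-sided alpha 0.05.

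**The concern.** One precision figure, estimated in one period with nearly everyone contributing, is applied to another period in which the plan expects most participants to be on dopaminergic therapy. If their scores are excluded, the wash-out slope rests on a fraction of the 135 per arm. SAP 3.6 recognises this loss, but the power statement in SAP 3.9 does not use it.

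SAP 2.1 uses the wash-in and wash-out comparisons to judge whether a slower decline reflects disease modification or a reversible symptomatic effect. A reader who takes the 80% at face value would give too much weight to a null censored wash-out result.

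There is also a labelling point. The 0.53 and the 0.65 are in original UPDRS units, whereas the trial outcome is MDS-UPDRS. SAP 3.8 converts by 1.29; SAP 3.9 does not. This leaves power unchanged but affects how the detectable difference is read.

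**Working it through.** **Inputs**

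- Phase 2 wash-in SE 0.53 with 25 per group; 135 per arm here (SAP 3.9).
- One-sided alpha 0.025, critical value 1.960 (SAP 6.6.8).
- Scale factor 1.29 (SAP 3.7).
- Untreated at month 24: about one-third, or 45 per arm (SAP 3.6). The 67% placebo figure for month 27 leaves a similar 33%.
- Lower retention: 100% − 70% − 8% = 22%, or 29.7 per arm (SAP 3.8).
- Dose-adjusted wash-out: 100% − 8% = 92%, or 124 per arm. This assumes no further loss after therapy starts.

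**Step 1. Reproduce the plan's figure**

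SE = 0.53 × sqrt(25/135) = 0.228.

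Power = Φ(0.65/0.228 − 1.960) = 81%.

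Difference detectable with 80% power = (1.960 + 0.842) × 0.228 = 0.64 UPDRS, or × 1.29 = 0.82 MDS-UPDRS units/month.

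The stated figure is therefore right for wash-in with everyone contributing. For 80% power at 0.65, the fraction contributing must be (0.639/0.65)² = 97%.

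**Step 2. Same formula with a fraction f contributing, SE = 0.228/sqrt(f)**

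This assumes that the wash-in per-subject variability carries over to wash-out.

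| Analysis | f | n per arm | SE (UPDRS) | Power at 0.65 | Detectable, UPDRS/month | Detectable, MDS-UPDRS/month |
|---|---|---|---|---|---|---|
| Wash-in | 1.00 | 135 | 0.228 | 81% | 0.64 | 0.82 |
| Wash-out, dose-adjusted | 0.92 | 124 | 0.238 | 78% | 0.67 | 0.86 |
| Wash-out, censored | 0.333 | 45 | 0.395 | 38% | 1.11 | 1.43 |
| Wash-out, censored | 0.22 | 30 | 0.486 | 27% | 1.36 | 1.76 |

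If placebo keeps one-third and active keeps 50% (the alternative in SAP 3.9), power is 44%, or 41% after 8% loss.

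**Step 3. Let the wash-out slope borrow from earlier visits**

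A change-point mixed model was evaluated with the subject-level components of SAP 3.8 (intercept 77.4, slope 0.230, covariance 2.87, residual 13.9), the planned visits, knots at 12 weeks and 24 months, and constant-hazard censoring.

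- No extra random slopes, 33% or 22% left at month 27: wash-out power 54% or 39%.
- Random segment slopes added so that the wash-in SE equals the plan's 0.228: 38% or 28%.
- Retention set at month 24 instead, extra segment-slope variance from 0 to 1: 36% to 49% at one-third, 24% to 34% at 22%.

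Overall this is about 25% to 55%. No run at this retention comes near 80%.

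**Step 4. The test for absence (bound 2.1, taken as MDS-UPDRS)**

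On the MDS-UPDRS scale the censored SEs are 0.395 × 1.29 = 0.510 and 0.486 × 1.29 = 0.627.

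- Power to declare absence when the true effect is zero: Φ(2.1/0.510 − 1.645) = 99% and Φ(2.1/0.627 − 1.645) = 96%.
- Power to detect a true effect of 2.1: Φ(2.1/0.510 − 1.960) = 98% and Φ(2.1/0.627 − 1.960) = 92%.
- If the true effect is 0.65 UPDRS (0.84 MDS-UPDRS), the chance of missing it and then declaring absence is about 19% at the SE of SAP 3.9, but 62% to 64% at the censored wash-out SEs.

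**The case against.** **The symptomatic model may not be censored.** SAP 6.6.8 and Protocol 10.5.8 do not say that scores after dopaminergic therapy are dropped. They name the as-treated sample, which SAP 6.2 censors on study-drug discontinuation. A reader might infer censoring from SAP 6.8.7, which lists "MDS-UPDRS I-III censored change at wash-in (per 6.6.8" as a predictor of treatment guesses. That line concerns wash-in at the week 6 questionnaire and does not settle how wash-out is handled. SAP 3.2 plans both versions, and the dose-adjusted one comes close to the stated power. This objection stands: the shortfall belongs to the censored version only.

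**Retention may be better than planned.** SAP 3.5 lets wash-out begin at the end of drug exposure if that is earlier, and SAP 6.6.8 defines the last segment as the "slope from 24 to 27 months (or from V10-equivalent visit on study drug to SV" visit. Earlier wash-outs under the closeout could leave more people untreated. The documents give no figure, so this can be noted but not quantified. In addition, the 67% is disability warranting therapy in the placebo arm rather than initiation, and the 22% uses the upper limit of the loss assumption.

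**No wash-out SE exists.** This also stands. The 27% to 38% range depends on the carried-over variability, which is why the wider mixed-model range is given.

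**The plan already warns of sparse data and hedges its wording.** SAP 3.6 does give the warning, and SAP 3.9 describes its figures as approximate. Approximate wording does not cover a fall from 80% to about 25% to 55%.

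**The consequence is small.** Largely accepted. The corrected detectable differences lie inside the 2.1 bound, so an effect of 0.65 UPDRS units/month is one that the plan's own margin tolerates.

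**Conclusion.** The power statement is correct for wash-in in UPDRS units and approximately correct for a dose-adjusted wash-out analysis that keeps about 92%. It is not correct for a wash-out analysis that excludes scores after dopaminergic therapy: there, power at 0.65 is about 27% to 38% with carried-over variability, or about 25% to 55% across mixed-model assumptions, at the 22% to 33% retention that the plan expects. The figures assume planned follow-up to month 27; the dose-adjusted figure also assumes that adjusted scores on therapy are as informative as untreated ones.

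A reader might go further and infer that the arithmetic in SAP 3.9 is wrong, that the whole symptomatic-effects test is underpowered, or that a disease-modification conclusion fails. The documents do not support this. The calculation reproduces, the test for absence keeps about 96% to 99% power at zero effect, and the disease-modification test in SAP 6.6.9 uses time to disability. The issue is minor to moderate: it concerns how much weight a null censored wash-out result can bear.

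**What to change.** In SAP 3.9, and in Protocol 10.3.3 if it is amended:

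1. Limit the 0.65 statement to wash-in, label it as UPDRS units, and add that the difference detectable with 80% power is about 0.82 MDS-UPDRS units/month.
2. Give wash-out its own statement that names the analysis. Censored: about 30 to 45 per arm, with about 1.4 to 1.8 MDS-UPDRS units/month detectable with 80% power, assuming the wash-in variability carries over. Dose-adjusted: about 0.86.
3. State in SAP 6.6.8 which of the two analyses its wash-out slope refers to, and say that earlier wash-outs under the closeout may change the numbers.
4. Note that these differences lie within the 2.1 points/month bound, so the test for absence keeps adequate power, and describe the censored wash-out result as supportive of wash-in.

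The cost is wording only. Sample size, data collection, alpha and the primary inference do not change; the stated wash-out power becomes less favourable.

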## 10.2.2.5 Two-period evaluations

Analysis of the persistence of benefit after the 3-month wash-out of period 2 among subjects randomized to active treatment during period 1 permits an evaluation of disease-modifying effect of serum urate elevation. Not all measures are amenable to two-period evaluation because of the censoring effect of initiation of dopaminergic therapy. In particular, with only one-third of subjects expected to have not initiated dopaminergic therapy at the end of period 1, few data on MDS-UPDRS trajectories during wash-out will be available and subjects contributing that data are a non-random subset of slow progressors. For other measures that are equally evaluable at the end of both periods, a three-part test of significantly

slower worsening during period 1, non-inferior rates of worsening during period 2, and a significant net benefit at the end of period 2 would provide evidence of disease modification if all three evaluations were favorable.

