Given preliminary data from SURE-PD on the variance components from random-slope models for MoCA after Rasch score conversion and S&E ADL, the effective standard deviations (in points per month) for these measures given our planned follow-up schedule are 0.038 and 0.31, respectively. Weaver et al. report an among-person standard deviation for PDQ-39 at 24 months after deep brain stimulation of 14.2 to 15.3. Assuming conservatively no within-person covariance, that would imply a standard deviation for 24-month change of approximately 30. Given these estimates, the trial will have 80% power to detect 2-year treatment differences on these outcomes as small as 0.31, 2.5, and 10.3, respectively.

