Given preliminary data from SURE-PD on the variance components from random-slope models for MoCA after Rasch score conversion, GDS-15, and S&E ADL, the effective standard deviations (in points per month) for these measures given our planned follow-up schedule are 0.038, 0.097, and 0.31, respectively. Weaver et al.¹³ report an among-person standard deviation for PDQ-39 at 24 months after deep brain stimulation of 14.2 to 15.3. Assuming conservatively no within-person covariance, that would imply a standard deviation for 24-month change of approximately 30. Given these estimates, the trial will have 80% power to detect 2-year treatment differences on these outcomes as small as 0.31, 0.80, 2.5, and 10.3, respectively.

4. Baseline Characteristics, Study Endpoints, and Final Disposition

4.1 **Baseline Characteristics**

Each analysis sample will be summarized overall and by treatment group for the following characteristics: randomization site; age, sex, race, ethnicity, time since symptom onset, time since PD diagnosis, modified Hoehn and Yahr score, resting tremor, use of an MAO-B inhibitor, serum urate, MDS-UPDRS scores, NeuroQoL module scores, years of education, MMSE, MOCA score, PDQ-39 score, modified Schwab and England ADL score, smoking history, caffeine consumption, sense of smell, RBD history, vigorous physical activity, serum urate, DAT ligand uptake, BMI, supine systolic and diastolic blood pressure, and orthostatic hypotension.

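### The PDQ-39 detectable difference uses an SD of change of 30 where zero covariance gives about 21; the 0.65 units/month figure is also claimed for wash-out at the full 135 per arm

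*SAP*

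**What the plan says.** **PDQ-39.** SAP 3.9 and Protocol 10.3.3 borrow a between-person SD of 14.2 to 15.3 at 24 months from a cited deep brain stimulation trial. They continue: "Assuming conservatively no within-person covariance, that would imply a standard deviation for 24-month change of approximately 30". From this and the slope SDs for the other scales, the SAP claims 80% power for "2-year treatment differences on these outcomes as small as 0.31, 0.80, 2.5, and 10.3, respectively". The protocol, which omits the depression scale, has "2-year treatment differences on these outcomes as small as 0.31, 2.5, and 10.3, respectively". PDQ-39 is the last entry in both lists.

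**Symptomatic effect.** The same sections take a phase 2 standard error of 0.53 UPDRS units/month, estimated during wash-in with 25 per arm, and scale it to 135 per arm (0.23). They then claim 80% power for a "difference in slopes during wash-in or wash-out of 0.65 units/month".

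**Who is left at wash-out.** Protocol 10.2.2.5 describes the start of wash-out "with only one-third of subjects expected to have not initiated dopaminergic therapy at the end of period 1". SAP 3.6 concludes that "few data on uncensored MDS-UPDRS trajectories during wash-out will be available". The primary power calculation in SAP 3.8 says: "We assume that 70% of subjects will initiate dopaminergic therapy based on experience in SURE-PD plus up to 8% additional lost to follow-up".

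**Handling of treated observations.** The spline model in SAP 6.6.8 does not say what happens to scores recorded after dopaminergic therapy starts. SAP 6.8.7 refers to the "MDS-UPDRS I-III censored change at wash-in (per 6.6.8) for response at the 6-week (V02) administration", which suggests censoring. SAP 3.2 plans both a version that excludes treated assessments and one that adjusts for LEDD.

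**The concern.** The PDQ-39 sentence contradicts itself. Zero covariance between the two time points gives an SD of change of sqrt(2) times the cross-sectional SD. A value near 30 is what results from adding the two SDs, which needs perfect negative correlation. PDQ-39 is a named secondary efficacy endpoint, so anyone judging a null result against the plan would think differences below 10.3 points were out of reach at 80% power. On the plan's own inputs, about 7 was detectable.

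The wash-out claim uses a sample size that the plan elsewhere says will not exist for a censored analysis. Wash-in and wash-out slopes are meant to help separate symptomatic from disease-modifying effects (SAP 2.1). A non-significant wash-out comparison should not be read against an 80% power statement that the plan does not support.

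**Working it through.** Inputs: 135 per arm (270 randomized 1:1, SAP 3.8) and 80% power. Alpha is not stated for these secondary figures. Two-sided 0.05 is assumed because it fits the four listed values best.

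**Reproducing the plan's list.** Detectable difference = (1.960 + 0.842) × SD × sqrt(2/135). The monthly slope SDs are multiplied by 24.

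| Outcome | SD over 24 months | Normal | t-based | Stated |
|---|---|---|---|---|
| MoCA | 0.038 × 24 | 0.311 | 0.312 | 0.31 |
| GDS-15 (SAP only) | 0.097 × 24 | 0.794 | 0.797 | 0.80 |
| S&E ADL | 0.31 × 24 | 2.54 | 2.55 | 2.5 |
| PDQ-39 | 30 | 10.23 | 10.27 | 10.3 |

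All four reproduce, so the method and n are as intended and the fault lies in the PDQ-39 SD.

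**SD of change with zero covariance.** SD of change = sqrt(SD0² + SD24²).
- sqrt(2) × 14.2 = 20.1
- sqrt(2) × 14.75 = 20.9
- sqrt(2) × 15.3 = 21.6

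The correlation needed for 30 at a cross-sectional SD of 15 is 1 − 900/(2 × 225) = −1. The plain sums of two SDs run from 28.4 to 30.6.

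**Corrected detectable difference (t-based, 135 per arm).** 6.9 at 20.1, 7.1 at 20.9 and 7.4 at 21.6. The stated 10.3 is therefore about 40 to 50% too large (10.3/7.4 = 1.39; 10.3/6.87 = 1.50). Power at 10.3 points is 98.8% at SD 20.1 and 97.5% at SD 21.6. With 8% loss (124 per arm) the range is 7.2 to 7.7. Alpha of 0.046 gives 6.9 to 7.5 (normal approximation). Neither variant approaches 10.3.

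**Reproducing 0.65.** 0.53 × sqrt(25/135) = 0.228, and 2.802 × 0.228 = 0.64. With the rounded 0.23 it is also 0.64, or 0.65 at alpha 0.046. The figure follows from the inputs at the full 135 per arm and stands for wash-in.

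**Wash-out, censored analysis.** The documents give no wash-out standard error. Assuming wash-in per-subject precision carries over, SE = 0.53 × sqrt(25/n):

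| Share uncensored | n per arm | SE | Detectable (UPDRS units/month) | Power at 0.65 |
|---|---|---|---|---|
| one-third | 45 | 0.395 | 1.11 | 38% |
| 30% (70% treated) | 40.5 | 0.416 | 1.17 | 34% |
| 22% (70% treated, 8% lost) | about 30 | 0.486 | 1.36 | 27% |

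**Effect on the non-inferiority step in SAP 6.6.8.** The bound of 2.1 points/month is on the MDS-UPDRS scale, so the SEs for 45 and 30 per arm are multiplied by 1.29, giving 0.51 to 0.63. With a true effect of zero and one-sided alpha 0.05, power is Φ(2.1/SE − 1.645), about 99% to 96%.

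**The case against.** The case against acting is mainly about weight. The PDQ-39 error is conservative, concerns one of many secondary endpoints reported with nominal p-values (SAP 6.6.10), and sits in planning text of a SAP that already refers to the October 2018 early-closeout notice. All of that is true, and it limits the consequence without making the figure right.

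The replacement value can also be questioned. It uses the full 135 per arm, and it is a change-score figure, whereas SAP 6.6.3 analyses continuous secondary endpoints with shared-baseline models. Under literal zero covariance, the shared-baseline repeated-measures model would rest on the cross-sectional SD: 2.802 × 14.2 × sqrt(2/135) = 4.8, and 5.2 at SD 15.3. The input SD also comes from a different patient population. These caveats stand. But the full-n convention is the one the plan uses for the companion figures, and the shared-baseline result moves still further from 10.3.

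On wash-out, the text is hedged, SAP 3.6 openly warns of sparse data, and the formal disease-modification test uses time to disability rather than slopes. SAP 6.6.8 also lets wash-out start at a V10-equivalent visit, when fewer subjects may be treated. SAP 3.9's own 62% placebo estimate at 24 months would leave 38% untreated. That share gives about 51 per arm, SE 0.370, a detectable difference of 1.04 and 42% power at 0.65. The V10-equivalent wording raises the untreated share by an unknown amount but does not restore 135 untreated per arm. It is fair that the wash-out magnitudes are illustrations: wash-out has one in-person MDS-UPDRS visit after month 24, whereas wash-in has three after baseline.

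**Conclusion.** Both parts hold. The PDQ-39 figure is wrong on its own stated assumption: the SD of change is 20.1 to 21.6 and the detectable difference 6.9 to 7.4 points, assuming two-sided alpha 0.05, 135 per arm and a two-sample comparison of change. This part is certain apart from the unstated alpha, which does not affect the conclusion.

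The 0.65 units/month figure is supported for wash-in only. For a wash-out analysis that censors at dopaminergic therapy, the 80% power statement conflicts with the plan's own expected numbers. The size of the shortfall (about 1.1 to 1.4 units/month, 27 to 38% power at 0.65) is conditional on wash-in precision carrying over. It does not apply to a LEDD-adjusted analysis, which would retain more subjects.

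Neither part affects the 270 subjects, the primary power, any test or any decision rule. On the same assumptions the non-inferiority step in SAP 6.6.8 would remain well powered if the true effect is zero. The correction should be made, but the trial does not depend on it.

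**What to change.** In SAP 3.9 and Protocol 10.3.3:
- Change the PDQ-39 SD of 24-month change from about 30 to about 21, and the detectable difference from 10.3 to about 7.1 (6.9 to 7.4). State that this is at 135 per arm and two-sided alpha 0.05.
- Restrict 0.65 units/month to wash-in.
- For wash-out, give the expected number per arm and a separate detectable difference, labelled as conditional on the assumed per-subject precision.

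In SAP 6.6.8, state whether observations after dopaminergic therapy are censored or LEDD-adjusted, so that the wash-out number follows from a defined analysis.

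The cost is one SD and one detectable difference edited in each document, plus a sentence or two on wash-out. Sample size, tests and conduct stay as they are.
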